90 stabilization surgery. Measurements of the aforementioned dependent variables will be taken
91 at time intervals of four weeks, eight weeks, 12 weeks, and six months post-operatively. It is
92 hypothesized that the inclusion of dry needling will result in an increase in range of motion,
93 increase in functional movement, and decrease in pain at an accelerated rate when compared
94 to rehabilitation alone. Findings will potentially lead to insights as to the benefit of applying
95 this intervention to additional body regions.
96

97 **2.2 Research Design**

98 The research design will be a single-blinded randomized controlled trial.
99

100 **2.3 Methodology /Technical Approach**

101 30-50 subjects at least four weeks after shoulder stabilization surgery will be
102 randomized into two groups (one experimental group and one control group). Subjects in the
103 experimental group will receive Trigger Point Dry Needling (TDN) intervention with
104 standard rehabilitation protocol (Appendix A) while subjects in the control group will receive
105 the same standard rehabilitation protocol without TDN. The experimental group will receive
106 trigger point dry needling one time per week for four to six weeks in addition to the standard
107 rehabilitation protocol. The control group will receive only the standard rehabilitation
108 protocol. Baseline measurements will be taken at approximately four weeks post operatively,
109 and subsequent measurements will be recorded at eight weeks, 12 weeks, and six months.

110 All patients who have undergone a shoulder stabilization procedure will be invited to
111 participate. Description of the study and informed consent will take place prior to
112 randomization. Concealed randomization will take place 0-7 days post-operatively.

113 At 4 weeks post-operatively, the following assessment tests will be undertaken:
114 supine shoulder flexion, supine shoulder external rotation, supine shoulder internal rotation,
115 functional movement testing, functional outcome measures, and the numeric pain rating
116 scale.^{1,2,3} Those subjects in the 'experimental group' will receive manual palpation of all
117 upper quarter muscles, including the cervical and thoracic spine region, to detect the presence
118 of myofascial trigger points (TPs). Dry needling will be performed to all detected TPs by a
119 provider trained and experienced in TDN.

120 In addition to the TDN intervention, the experimental group subjects will undergo a

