504 BASELINE DEMOGRAPHIC COLLECTION AND EVALUATION – POST OP DAY ~7 505 Subject recruitment

506 Subjects will be screened for inclusion/exclusion criteria.

507 Subjects will be given a random numeric identifier.

508 All data will be recorded and stored by individual numeric identifier. Group assignment will
509 be kept separate and will only be known by PI or AI.

510 Subjects meeting all entrance criteria, to include standardized physical exam, will be
511 consented, numeric identifier given, and group assignment provided. Demographic
512 information will be recorded to include age, gender, duration and location of symptoms. The
513 physical exam will be in accordance with the post-operative protocol and is standard of care
514 after these procedures. Elements may include evaluation of neurological status,
515 neurovascular integrity, wound healing, and assessment of joint mobility. Data from the
516 initial physical exam is only used for clinical purposes. Both the experimental and control
517 groups will receive physical therapy in accordance with the post-operative protocol until their
518 4 week follow up. No TDN will be performed at this time post-operatively, baseline
519 demographics only.
520
521
522

523
524
525 4 WEEKS POST-OPERATIVE:
526 Initial Data Collection
527 The outcome assessor performing data collection and measurements will remain blinded to
528 group assignment. In both the experimental and control groups, they will test and record
529 ROM of glenohumeral internal rotation, external rotation, flexion, and functional movement
530 of the shoulder. Each subject will complete the Global Rating of Change survey (GROC),
531 Patient Specific Functional Scale (PSFS), and Shoulder Pain and Disability Index (SPADI).
532 Subjects will be asked to report compliance with home exercise program by presenting his or
533 her exercise log. Pain level will be recorded using the NPRS. No TDN will be performed at
534 this time post-operatively, data collection only.
535
536 EXPERIMENTAL GROUP TDN TREATMENTS #1-4, 4-8 WEEKS POST-OPERATIVE
537 TDN will be performed to all detected TPs in experimental group only by PI or AI's. As part
538 of the standard course of treatment, both the experimental and control groups will participate
539 in supervised rehabilitation in accordance with the post-operative rehabilitation protocol
540 throughout this time period.
541
542 8 WEEKS POST-OPERATIVE
543 Follow Up Data Collection

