 603 a locked filing cabinet, behind a locked door. Signed consent forms, group assignment, and
 604 data collection forms will all be kept in separate folders and filing cabinet drawers. All
 605 electronic study databases will be secured on password protected computers and stored on a
 606 server with restricted access requiring CAC authentication. Subject data will only be
 607 identified by each subject's identification code.

608

609

610 **6.3.5 Study Time Line**

611

612 **Demographic/ Data Collection and Intervention Timeline**

613

614

	Baseline	4 weeks	Tx 1-4; Experimental Group Only	8 weeks	12 weeks	6 months
Informed Consent, Discuss Plan, etc	x					
Screening, Demographics	x					
Randomization	x					

History and Physical		x		x	x	x
TDN to Experimental group			x			
HEP Instruction	x	x		x	x	x
ROM Measurement		x		x	x	x
GROC	x	x		x	x	x
PSFS	x	x		x	x	x
NPRS	x	x		x	x	x
SPADI	x	x		x	x	x

615

616

617 **6.4 Statistical Consideration**

618 Descriptive statistics will be provided. Data analysis will be performed with statistical
 619 analysis software R version 3.1.2. A 2x4 repeated measures ANOVA with Sidak's post hoc
 620 testing will be used with time as the within-subjects factor and group (control or TDN) as the
 621 between-subjects factor.

622

623 **6.4.1 The primary endpoints (i.e., primary outcome variables) and the secondary**
 624 **endpoints, if any.** Clearly define primary and secondary outcome variables of the research
 625 study.

626 Outcome variables for this study are as follows:

627 **Primary Outcomes:**

1. **Passive Range of Motion:** Changes in range of motion of the shoulder, as measured by glenohumeral range of motion during passive shoulder flexion, external rotation, and internal rotation, and are necessary outcome variables to determine the effectiveness of dry needling of shoulder TPs in a post-operative population.⁸
2. **Shoulder Functional Movement Test:** To assess overall change in movement mechanics of the shoulder. Functional Movement patterns are needed to perform complex tasks such as pull-ups and pushups.³
3. **Numeric Pain Rating Scale (NPRS):** Severity of pain in the shoulder with functional activities at each visit will be assessed using a scale from 0-10. The subject will report their level of pain with the instruction that "0 is no pain, 10 is the worst pain imaginable".^{6,18}

640 **Secondary Outcomes:**

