1. **Global Rating of Change score:** To assess overall change from initial presentation, the GROC will be recorded at each follow up visit. This score is rated from -7 to +7 where subjects will select an answer that best describes their current perceived status since injury onset.^{23,45}
2. **PSFS:** The PSFS is a self-report questionnaire assessing pain, instability and activities of daily living (ADLs).⁶
3. **SPADI:** The SPADI is a self-report questionnaire assessing pain and

648 disability.^{48,49}

649 4.

650

651 6.4.2 Data analysis

652

653 Descriptive statistics will be provided. Data analysis will be performed with statistical
654 analysis software R version 3.1.2. A 2x4 repeated measures ANOVA with Sidak's post hoc
655 testing will be used with time as the within-subjects factor and group (control or TDN) as the
656 between-subjects factor. Alpha will be = .05.

657

658 6.4.3 Safety Monitoring and Analysis Plan.

659 For this study, continuous assessment of participant's response to treatment will be
660 performed, especially their response to dry needling techniques. If the participant experiences
661 soreness greater than expected or has hematoma develop increasing in size then needling
662 techniques will be discontinued. At any time the subject can elect to discontinue participation
663 in the study and will continue with standard of care treatment.

664

665 6.4.4 Sample Size Estimation

666

667 30-50 status post shoulder stabilization surgery meeting inclusion and exclusion criteria will
668 be recruited for this study. A priori sample size calculation using G Power 3.1.2 was
669 performed and it was determined the required sample size would be 34 subjects. This sample
670 size provides 80% power to detect an effect size of 1.0 at the eight week follow-up with an
671 alpha level of .05. To account for a potential 10-15% of subjects lost to follow-up, 38
672 subjects is the goal for recruitment.¹⁴ Multiple prior studies on TDN of upper quarter
673 musculoskeletal disorders have reported very large changes (effect sizes > 1.5) in range of
674 motion after TDN.^{20,27}

675

676 6.5 Reporting Adverse Events

677

678 6.5.1 Expected Adverse Events from Research Risks and Reporting Describe the
679 expected adverse events from research risks using the following categories (the event
680 rates may be derived from your clinical experience or literature).

681

- Rare but serious (Event Rate < 1%):

Collapsing Lung

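### The 80% power in section 6.4.4 belongs to an unadjusted week-8 t test that the analysis section does not name; a named week-8 contrast adjusted for the week-4 baseline would fit it, once the needling schedule is reconciled

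*Combined protocol and SAP*

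**What the plan says.** Sections 6.4 and 6.4.2 describe the inferential analysis in the same terms: "A 2x4 repeated measures ANOVA with Sidak's post hoc" "testing will be used with time as the within-subjects factor and group (control or TDN) as the" between-subjects factor. Section 6.4.2 adds an alpha of .05. Neither section says whether the group effect, the group-by-time interaction or a post hoc comparison decides the trial, which comparisons the Sidak correction covers, or whether any covariate is used.

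The study-variables table in section 6.3.4 lists week 4 as the first of four levels of time. Section 2.3 treats that visit as baseline: "Baseline measurements will be taken at approximately four weeks post operatively". Section 6.3.2 confirms that it is for data collection only and that needling comes afterwards.

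Section 6.4.4 rests on a single time point. The sample "size provides 80% power to detect an effect size of 1.0 at the eight week follow-up with an" alpha of .05, for 34 subjects.

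The documents differ on how long needling lasts. Section 2.3 gives "trigger point dry needling one time per week for four to six weeks in addition to the standard" protocol. Section 6.3.2 has "EXPERIMENTAL GROUP TDN TREATMENTS #1-4, 4-8 WEEKS POST-OPERATIVE", and the timeline in section 6.3.5 has "Tx 1-4; Experimental Group Only" between the week-4 and week-8 visits.

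**The concern.** The sample size is justified by one test and the analysis section describes others. A 2x4 ANOVA offers at least three routes to a claim: the group main effect, the interaction, and a Sidak-corrected comparison at week 8. Their power differs widely with the between-visit correlation and the shape of the effect over time. With none named, the choice could be made after the data are seen, and a reader could not tell.

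Week 4 cannot carry a needling effect. The interaction uses it implicitly, as the reference for change. The group main effect averages it in with the follow-up visits and is diluted by it. The value is already collected, and used as a covariate it could sharpen the week-8 comparison at almost no cost.

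**Working it through.** **Inputs.** From section 6.4.4: 34 subjects, effect size d = 1.0 at week 8, alpha .05, 80% power. Assumed: two-sided test, 1:1 allocation (n = 17 per arm), d in units of the week-8 standard deviation, complete data, one outcome. The documents give no between-visit correlation ρ, so 0, 0.3, 0.5 and 0.7 are used, with equal variances and equal correlations across visits.

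**1. The plan's own figure.** Two-sample t test, noncentrality d√(n/2).
- 17 per arm: 1.0 × √8.5 = 2.915 on 32 df, power 80.7%.
- 16 per arm: 1.0 × √8 = 2.828 on 30 df, power 78.1%.

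So 34 is the smallest balanced total that reaches 80%, with no covariate and no multiplicity correction.

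**2. The same week-8 comparison with Sidak.** Per-comparison alpha is 1 − 0.95^(1/k).
- k = 3: .01695, power 65%.
- k = 4: .01274, power 61%.
- k = 6: .00851, power 55%.

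**3. The ANOVA effects.** Let δ be the group difference at each of the four visits.
- Main effect: standardised effect mean(δ)/√((1+3ρ)/4), 32 df.
- Interaction: noncentrality (17/2) Σ(δ − mean δ)²/(1−ρ), on 3 and 96 df.

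At ρ = 0.5:
- Sustained effect, δ = (0, 1, 1, 1). Main effect: 0.75/√0.625 = 0.949, power 77%. Interaction: 8.5 × 0.75/0.5 = 12.75, power 85%.
- Week-8-only effect, δ = (0, 1, 0, 0). Main effect: 0.25/√0.625 = 0.316, power 15%. Interaction: the sum of squares is again 0.75, so 85%.

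**4. Week-8 contrast adjusted for week 4.** Noncentrality d√(17/2)/√((1−ρ²)(1+F/32)), averaged over F ~ F(1,32) to allow for chance imbalance at week 4, on 31 df.

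| Test (d = 1.0 at week 8) | ρ = 0 | 0.3 | 0.5 | 0.7 |
|---|---|---|---|---|
| Unadjusted week 8 | 81% | 81% | 81% | 81% |
| Adjusted week 8 | 79% | 83% | 89% | 97% |
| Main effect, sustained | 99% | 87% | 77% | 67% |
| Interaction, sustained | 53% | 70% | 85% | 98% |

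The largest loss against the unadjusted test is at ρ = 0: 80.7 − 79.4 = 1.3 points. The two are equal at ρ = 0.184. With a sustained effect the main effect and the adjusted contrast are equal at ρ = 0.349. A simulation of 40,000 trials per correlation agreed with the adjusted figures to within half a point.

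**5. If the effect is still building at week 8** (ρ = 0 / 0.3 / 0.5 / 0.7).
- Differences of 0.3, 0.6 and 1.0 at the three follow-ups: adjusted week-8 contrast 13 / 14 / 16 / 22%, planned interaction 40 / 55 / 71 / 92%. A joint 3-df test of the three adjusted differences has 78 / 71 / 78 / 92%.
- Six weekly sessions with the effect proportional to sessions given (an assumption: 4/6 = 0.67 at week 8, then 1.0): adjusted week-8 contrast 46 / 49 / 57 / 74%, planned interaction 48 / 64 / 80 / 96%.

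**The case against.** A pre-treatment level in a 2x4 design is conventional, and the group-by-time interaction already uses week 4. Both points stand. A reader might infer that the plan ignores its baseline or that the ANOVA is invalid; the documents support neither.

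A reader might also infer that the adjusted contrast is simply more powerful than the plan. It is not. The threshold of about 0.18 is against the unadjusted week-8 t test only. With a sustained effect the main effect is stronger below a correlation of about 0.35, and the interaction is stronger when the effect is still building at week 8. In the sustained case at least one planned test exceeds 80% at each correlation tabulated. The difficulty is that the plan does not say in advance which one counts.

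The Sidak figures take one reading of the post hoc test, a cross-sectional comparison at week 8. Section 6.4.2 equally allows a comparison of change from week 4. With noncentrality d√(n/2)/√(2(1−ρ)), 96 df and 3 contrasts, that has 36 / 52 / 69 / 91% at ρ = 0 / 0.3 / 0.5 / 0.7. Part of the apparent gain over Sidak also comes from testing at the full .05. At the 3-contrast Sidak alpha, the adjusted contrast has 64% at ρ = 0 and 78% at ρ = 0.5. This stands, and the power statement must say which alpha it uses.

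Finally, the choice of week 8 depends on a treatment schedule that the documents leave inconsistent. This stands too, and it comes first in the fix.

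**Conclusion.** The concern holds in a limited form. Section 6.4.4 powers an unadjusted two-group comparison at week 8, and sections 6.4 and 6.4.2 do not name that test or any other decisive one. The mismatch does not depend on the unknown correlation. Its size does: at a correlation of 0.5, the planned routes run from 15% (main effect, week-8-only effect) to 85% (interaction), with 55 to 65% for the cross-sectional Sidak comparison.

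Adjusting a named week-8 contrast for week 4 is a sound and nearly free improvement on the test behind the power statement: at worst 1.3 points lower, and 89% against 81% at a correlation of 0.5. All these figures assume two-sided testing, 1:1 allocation, d in week-8 standard deviations, complete data and one outcome at alpha .05. A reader might conclude that the trial is underpowered. That does not follow, because the stated figure is correct for the test it describes. The trial remains analysable, but the decisive test should be fixed before group assignment is joined to the data. Confidence is medium, because the correlation and the time course of the effect are unknown.

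**What to change.** 1. First reconcile section 2.3 with sections 6.3.2 and 6.3.5 on the number of sessions. If week 8 may precede the end of needling, re-justify the primary time point and restate its power.
2. For the continuous outcomes (range of motion, NPRS, PSFS, SPADI), specify the week-8 group contrast adjusted for the week-4 value, and name it as the primary analysis that matches section 6.4.4. Use an ANCOVA, or its equivalent in a model of weeks 8, 12 and 6 months with group, visit, group-by-visit, week-4 value and week-4-by-visit. The group coefficient is the same for the week-8 value or the change from week 4, so it still addresses range of motion as worded in section 6.4.1. An early difference also fits the hypothesis in section 2.1 of an "increase in functional movement, and decrease in pain at an accelerated rate when compared" to rehabilitation alone.
3. Report as secondary: the week-12 and 6-month differences, the adjusted average over the three follow-ups, and the joint 3-df test of the three adjusted differences. The joint test covers an effect that grows.
4. State in section 6.4.4 that the power is for one outcome at unadjusted alpha .05. Restate it if a Sidak correction, or sharing of alpha across the several primary outcomes, applies to this contrast.
5. State that week 4 is the covariate. Sections 6.3.4 and 6.3.5 also list an earlier baseline for NPRS, and section 6.3.5 does so for PSFS and SPADI. Note that week 4 follows randomization (days 0 to 7, section 2.3), so the adjustment assumes that knowing the group did not alter the week-4 value.

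The ordinal functional tests and GROC are outside this change and need their own analysis.

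Cost: rewording of sections 6.4, 6.4.2 and 6.4.4, with no new data, visits or subjects. With complete data the primary contrast is an ordinary linear model in base R. Only the multi-visit model needs a mixed-model package, whose support in the named R version should be checked.

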359 human participants will yield the most applicable and generalizable results.

360 Dry needling has been shown to have minimal risk to subjects with reported
361 frequency of significant adverse effects occurring in less than 1% of sessions.^{17, 43} The
362 most common adverse effects are post needling soreness, hematoma at needling site and
363 pain.^{17, 43, 44} The application of dry needling to the protocol and conducting on human
364 subjects is reasonable and risks to the subjects are minimal.

366 6. PLAN

368 6.1 New Investigational Drugs/Investigational Devices Exemption Status 369 N/A

371 6.2 Selection of Subjects

373 6.2.1 Type of the Subject Population

375 Participants for this study will be Department of Defense (DOD) healthcare beneficiaries at
376 West Point and Keller Army Community Hospital age 18 years to 40 presenting status post
377 shoulder stabilization repair surgery. In the event that an emancipated, 17 year old cadet
378 meets inclusion criteria for the study, they will also be allowed to participate.

380 6.2.2 Inclusion and Exclusion Criteria

Inclusion	Exclusion
Age 18-40 DOD beneficiaries (17 if Cadet)	Self-Reported Pregnancy
Status post shoulder stabilization repair surgery	History of blood borne pathogens/infectious disease/active infection/metal allergy
	Bleeding disorders or currently taking anti- coagulant medications
	Participants who are not fluent in English

382
383
384 The PI is not fluent in languages other than English and is unable to have study materials
385 translated and certified in other languages. For this reason, we are not able to
386 accommodate participants who speak languages other than English.

388 6.2.3 Recruitment

389 a. Subject selection must be equitable.

391 There is a high feasibility of recruiting 30-50 subjects for this study within an
392 eight month timeframe. This is based on the number of shoulder stabilization
393 procedures performed at Keller Army Hospital that average 8 per month. To our
394 knowledge, the other studies that involve this population do not include subjects
395 status post shoulder stabilization repair and are not receiving TDN. There is a low
396 likelihood that subjects able to participate in our study will already be participating in
397 another injury study of this nature.

398 Given the inclusion and exclusion criteria, any subject that presents status post
399 shoulder stabilization repair has the possibility of being recruited into the study. We

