580 administered, if any. As appropriate, include the validity and reliability of the instruments.
581 For subject's confidentiality protection, outline the procedure for coding, recording, storing
582 and protecting the data. Provide a copy of data collection sheets, case report forms, survey
583 forms/questionnaires/instruments, and/or a copy of the author's permission granting the use
584 of the instruments in the *Appendix Section 20*.

585

586 All data will be collected through survey questions and direct researcher measurements.

587

588

589

590

591 Data collected and Time Points

SURVEY DATA	OBJECTIVE MEASUREMENTS
Age -baseline demographic questionnaire	Glenohumeral Internal Rotation - initial data collection, at each follow up
Gender -baseline demographic questionnaire	Glenohumeral External Rotation - initial data collection, at each follow up
Duration of symptoms -baseline demographic questionnaire	Glenohumeral Flexion - initial data collection, at each follow up
Numeric Pain Rating Scale (NPRS) for shoulder pain -baseline demographic questionnaire - initial data collection, at each follow up	Functional Range of Motion Test - initial data collection, at each follow up
	Global Rating of Change (GROC) -at each follow up
	PSFS -initial data collection, at each follow up
	SPADI -initial data collection, at each follow up

592

593 Study Variables

INDEPENDENT VARIABLES	DEPENDENT VARIABLE
Group Assignment (2 Levels) 
 - Experimental - Control 	Shoulder Range of Motion 
 -Internal Rotation (degrees) - External Rotation (degrees) - Flexion (degrees) -Functional Movement Test
Time (4 Levels) 
 - Week Four - Week Eight - Week 12 - Month Six 	Shoulder pain (NPRS) 
 -with internal rotation - with external rotation - with flexion - with functional movement test
	GROC
	PSFS
	SPADI

594

595

596 Data Collection/Confidentiality

597 Subjects will sign the consent forms but no identifiable information will be on data collection
 598 forms. Each of the subjects will be randomly assigned a subject identification number from
 599 1-38 upon entrance into the study and subsequently given consent forms and survey/data
 600 collection forms with the corresponding number. Each number assigned will only be used
 601 once.

602 All subject information and data collection forms will be kept behind double locks: in

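### The 30-50 recruitment range starts below the plan's own requirement of 34 subjects, and the goal of 38 covers only the 10% end of the stated 10-15% loss

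*Combined protocol and SAP*

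**What the plan says.** Section 6.4.4 (Sample Size Estimation) gives three sizes in one paragraph.

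- A range: "30-50 status post shoulder stabilization surgery meeting inclusion and exclusion criteria will" be recruited.
- A requirement from a G*Power calculation: "performed and it was determined the required sample size would be 34 subjects. This sample" "size provides 80% power to detect an effect size of 1.0 at the eight week follow-up with an" alpha of .05.
- A goal that allows for dropout: "alpha level of .05. To account for a potential 10-15% of subjects lost to follow-up, 38" "subjects is the goal for recruitment".

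The range appears twice more. Section 2.3 gives it as the number to be randomized ("30-50 subjects at least four weeks after shoulder stabilization surgery will be"), and section 6.2.3 uses it in the feasibility statement ("There is a high feasibility of recruiting 30-50 subjects for this study within an" eight-month period). Sections 6.3.4 and 6.7 number subjects from 1 to 38, each number used once. No section says how the range relates to 34 or 38.

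**The concern.** A sample size section should leave one answer to the question of how many subjects to enrol. Here the opening sentence permits totals that the next sentences rule out. A team that stopped at 30 would be inside the range but four short of the stated requirement before any dropout. Falling short is a realistic prospect, because the scientific review appended to the protocol names the time limit as the study's biggest challenge.

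The dropout allowance raises a second, smaller question. The plan presents 38 as the answer to a loss of 10-15%, and whether 38 covers that whole interval can be checked by division.

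**Working it through.** **Inputs.** From section 6.4.4: 34 required, 80% power, effect size 1.0 at week 8, alpha .05, loss 10-15%, goal 38, range 30-50. From section 2.3: two groups. The plan does not state the test, its sidedness, the allocation ratio or the type of effect size. I assume a two-sample t-test, two-sided, 1:1, with Cohen's d = 1.0.

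**Formula.** Power from the noncentral t distribution with n1 + n2 - 2 degrees of freedom and noncentrality d × √(n1·n2/(n1 + n2)).

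**The plan's own figure.** With 17 per arm the noncentrality is √(289/34) = √8.5 = 2.915 and power is 80.7%. This is the smallest equal-arm design that reaches 80%, so 34 reproduces. A one-sided test would need only 14 per arm, 28 in all, so it is not the calculation behind 34.

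**The dropout allowance.** 34/0.90 = 37.8, which rounds up to 38. 34/0.85 = 40. The largest loss that 38 can absorb and still keep 34 is 4/38 = 10.5%.

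**Power at the figures in the plan:**

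| Recruited | Loss | Remaining | Noncentrality | Power |
|---|---|---|---|---|
| 30 | none | 30 (15 + 15) | √7.5 = 2.739 | 75.3% |
| 30 | 10% | 27 (13 + 14) | √(182/27) = 2.596 | 70.4% |
| 30 | 15% | 25 (12 + 13) | √(156/25) = 2.498 | 66.7% |
| 38 | 10% | 34 (17 + 17) | √8.5 = 2.915 | 80.7% |
| 38 | 15% | 32 (16 + 16) | √8 = 2.828 | 78.1% |

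In the third row 30 × 0.85 = 25.5 is rounded down; with 26 remaining, power is 68.7%.

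**Reading across the range.** From 30 to 33 recruited, 34 cannot be reached at all. From 34 to 37, it is reached only if loss stays under the plan's own 10%: at 37, for example, loss may be at most 3/37 = 8.1%. At 38, it is reached at the lower end of the stated loss but not at 15%. Above 38, power is not the difficulty (50 with no loss gives 93.4%), but the identifier list runs out.

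**The case against.** The best defence is that the plan does name a target. It calls 34 required and 38 the goal, and the identifiers 1-38 agree with that goal. Both figures lie inside 30-50, and in section 6.2.3 the range is only a statement of feasibility. Much of this stands: the range conflicts with the other figures at its ends, not throughout. It does not remove the conflict, because sections 6.4.4 and 2.3 use the range for the numbers to be recruited and randomized, and nothing tells the reader to disregard its lower end.

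A reader might go further and infer that the trial may close at 30 and still claim 80% power. The text does not support that. It attaches the 80% to 34, never claims it for 30, and gives no rule for closing at 30.

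A reader might also treat 38 as a failed allowance. That is too strong: 10.5% lies within the stated interval, and the shortfall at 15% is under two percentage points of power. The 10-15% is not tied to week 8 either. Follow-up runs to six months, so applying the full loss at week 8 is a worst case.

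Finally, a reader might infer from the identifiers that a 39th subject could not be enrolled. That is an administrative matter of lengthening a list and has no bearing on power or validity.

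**Conclusion.** The concern holds in a limited form. The lower end of the range, 30 to 33, is below the plan's stated requirement whatever the dropout. At 30, power is about 75% with no loss and about 67-70% at the stated loss, against 80% intended. Separately, 38 delivers the intended power at about 10% loss and about 78% at 15%.

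That 30 to 33 is below 34 needs no assumption. The power figures rest on the two-sided, 1:1, Cohen's d reading, which is inferred because it reproduces 34. They describe one two-group comparison at week 8. They say nothing about power for the planned 2x4 repeated measures ANOVA or across the several primary outcomes. The underlying calculation is sound; what needs correcting is the wording around it.

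**What to change.** Replace the range in sections 2.3, 6.2.3 and 6.4.4 with the single stated goal of 38. The feasibility statement survives the change: at the stated average of 8 procedures a month over eight months there are 8 × 8 = 64 candidates, of whom 38 is 59%.

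In section 6.4.4, restate the allowance along these lines, once the investigators confirm the test, sidedness and allocation ratio that they used:

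*38 covers about 10% loss (34 subjects, 81% power for a single two-group comparison at week 8, two-sided t-test, effect size 1.0); if loss by week 8 reaches 15%, about 32 remain and power is about 78%.*

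If the investigators prefer to cover 15% in full, the target is 40. In that case, or if enrolment above 38 is to be allowed for any other reason, extend the identifier list in sections 6.3.4 and 6.7 to match.

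Keeping 38 is a change of wording only. The price is that the stated power at 15% loss looks slightly less favourable than the present text suggests.

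### Section 6.4.4: 38 recruits cover about 10% loss, not 10-15%, and the 80% power matches an unadjusted week-8 comparison with no allowance for the planned Sidak tests

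*Combined protocol and SAP*

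**What the plan says.** Section 6.4.4 (Sample Size Estimation) reports that an a priori G*Power calculation was "performed and it was determined the required sample size would be 34 subjects". At an alpha of .05 this is said to give "80% power to detect an effect size of 1.0 at the eight week follow-up". The recruitment goal is then set at 38 to absorb a loss to follow-up of 10-15%. The section names no test, sidedness, specific outcome or multiplicity allowance. In support of the effect size it cites earlier studies of needling in upper-quarter disorders: "musculoskeletal disorders have reported very large changes (effect sizes > 1.5) in range of" motion.

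The analysis is set out in 6.4 and again in 6.4.2: "A 2x4 repeated measures ANOVA with Sidak's post hoc" testing, with time within subjects, group between subjects and alpha .05. Neither section says which comparisons the Sidak adjustment covers. Section 6.3.4 gives two groups and four time levels (weeks 4, 8 and 12, and month 6). Section 6.4.1 lists three primary outcomes. The first is described as "Changes in range of motion of the shoulder, as measured by glenohumeral range of motion" in flexion, external rotation and internal rotation; the others are a functional movement test and pain on the NPRS.

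**The concern.** Two statements in 6.4.4 do not follow from the rest of the plan.

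The first is the loss allowance. Dividing 34 by the retained fraction gives 38 only at the lower end of the stated range.

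The second is the power. In the planned ANOVA, a group difference at week 8 is a post hoc contrast, and post hoc tests are to be Sidak-adjusted. A sample size calculated for one comparison at alpha .05 gives the stated power for that contrast only if the adjustment leaves alpha at .05. Whether it does depends on the family, which the plan does not define.

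At stake is how the 80% is read. A reader will take it as the power of the planned week-8 comparison, with up to 15% loss already covered. The plan as written secures neither.

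**Working it through.** **Inputs.** From 6.4.4: 34 subjects, effect size 1.0, week 8, alpha .05, 80% power, 38 recruits, 10-15% loss. From 6.3.4: two groups, four time levels. Assumed, because not stated: equal allocation, effect size 1.0 read as a group difference of one SD of the week-8 score, two-sided tests.

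**Step 1: reproduce the plan's figure.** For a two-sample t-test with n per group, the noncentrality is d × √(n/2) and df = 2n − 2.
- n = 17: noncentrality 1.0 × √8.5 = 2.915, df 32, two-sided alpha .05: power 80.7%.
- n = 16: noncentrality √8 = 2.828, df 30: power 78.1%.
- One-sided at .05: 13 per group gives 79.7% and 14 per group gives 82.4%, so the total would be 28.

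So 2 × 17 = 34 is the smallest equal-arm total that reaches 80% with one unadjusted two-sided t-test. The match is exact, but the test is inferred.

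**Step 2: loss to follow-up.** Recruits needed = 34/(1 − loss).
- 10% loss: 34/0.90 = 37.8, so 38.
- 15% loss: 34/0.85 = 40.
- Largest loss that 38 can bear: (38 − 34)/38 = 4/38 = 10.5%.
- 38 recruits at 15% loss: 38 × 0.85 = 32.3, so about 32 complete. From step 1, 16 per group gives 78.1% unadjusted, if all the loss has occurred by week 8 and only completers are analysed.

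**Step 3: Sidak-adjusted power of the raw week-8 group contrast, 17 per group, d = 1.0.** Adjusted alpha = 1 − 0.95^(1/k) for k comparisons. Two error terms are shown because the plan does not say which applies.
- Stand-alone: the week-8 t-test, df 32.
- Pooled: the ANOVA's between- and within-subject errors combined. Under compound symmetry with correlation r, these have expected mean squares 1 + 3r (32 df) and 1 − r (96 df). The Satterthwaite df is 16/[(1 + 3r)²/32 + (3(1 − r))²/96]. For r = .3 this is 16/(3.61/32 + 4.41/96) = 101; for r = .7 it is 16/(9.61/32 + 0.81/96) = 52. The range r = .3 to .7 is an assumption.

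| Comparisons in family (k) | Adjusted alpha | Stand-alone t | Pooled error (r = .7 to .3) |
|---|---|---|---|
| 1 | .0500 | 80.7% | 82% |
| 2 | .0253 | 71.4% | 73-74% |
| 3 | .0170 | 65.4% | 67-69% |
| 4 | .0127 | 61.1% | 63-65% |

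A family of three would correspond to the three post-treatment visits, and a family of four to all four time levels. The documents specify neither.

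**The case against.** The strongest reply is that 6.4.4 contains no error of power arithmetic. The 34 and the 80% reproduce exactly, and with only two groups there is one between-group comparison at each visit. If Sidak is applied within each visit, k = 1 and the stated power stands. This is a natural reading and it is accepted. What remains is that the plan does not say so, and any family larger than one brings the raw week-8 contrast below 80% under either error term.

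Second, the outcome is not wholly unidentified, because the supporting sentence concerns range of motion. That stands in part: 6.4.1 lists three directions of motion, and 6.4.4 does not say which one the 80% refers to.

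Third, the loss shortfall is small: two recruits, and 80.7% against 78.1%. That is correct. Also, follow-up runs to six months, so some of the loss may come after week 8 and week-8 power would then fall by less. The sentence in 6.4.4 is still wrong for the upper part of its own range.

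Fourth, the 30-50 recruitment range in 2.3, 6.2.3 and 6.4.4 includes 40. It does, and there is no reason to narrow it. But the stated goal is 38, and the subject numbers in 6.3.4 and 6.7 also stop at 38.

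A reader might go further and infer that the trial is underpowered. The documents do not support that. Power for the planned analysis depends on the Sidak family, the error term, the correlation between visits and the scale on which 1.0 is standardised, and none of these is given. If 1.0 is an SD of change, for example, a single unadjusted comparison of change has 80.7% power whatever the correlation.

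**Conclusion.** The point holds, in two parts of different weight.

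The loss allowance is wrong as written: 38 recruits cover up to 10.5% loss, and 15% needs 40. The effect is small, about 2.6 percentage points of unadjusted power (80.7 − 78.1), and assumes that all loss occurs by week 8.

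The power statement is unsupported rather than wrong. It is right for an unadjusted two-sided week-8 comparison, and for the planned contrast if Sidak covers one comparison per visit. If the family is two, three or four comparisons, the raw week-8 contrast has about 71-74%, 65-69% or 61-65% power. These figures assume 17 per group, d = 1.0 in raw-score SD units and, for the upper values, compound symmetry with correlation .3 to .7. This is a shortfall in what the plan states, not evidence that the trial as a whole lacks power. It should be fixed.

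**What to change.** Keep the 2x4 ANOVA and change the text only.

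1. In 6.4.4, replace the loss statement with wording such as: *Recruiting 38 covers about 10% loss (34 complete); at 15% loss about 32 complete, and unadjusted power at eight weeks is about 78%.*

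2. For the power statement, take one of two routes.
   - In 6.4.4, say what the 80% is: *The 80% refers to an unadjusted two-sided comparison of [named outcome, with direction if range of motion] at eight weeks.*
   - Or, in 6.4.2, list the comparisons that the Sidak adjustment covers for each outcome, and in 6.4.4 restate the power of the week-8 contrast at that adjusted alpha, giving the outcome and the error term. If the family is one comparison per visit, saying so is enough to retain the 80%.

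Neither route needs more patients or a different analysis. The investigators must commit to a named outcome and, on the second route, to a Sidak family. The only downside is a less favourable stated figure: about 78% at 15% loss and, if the family exceeds one comparison, the adjusted power shown above.
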